Tumor response will also be determined by the Investigator based on irRECIST ([Bohnsack, 2014](#)) as an exploratory assessment. Other exploratory efficacy variables, such as ECOG PS, alpha-fetoprotein (AFP) reduction, etc, will be summarized as well. An independent review of the efficacy results may take place at any time during the study.

Following disease progression, survival status will be determined approximately every 3 months thereafter until 2 years from enrollment, lost to follow-up, death or withdrawal of consent, whichever occurs sooner.

New anticancer therapies will also be collected at the same schedule. New anticancer therapy includes (but is not limited to) any systemic or locoregional medication, surgery, radiation, or any other therapy intended to treat the subject's cancer.

Overview of Key Safety Assessments

All subjects will be monitored for adverse events (AEs), starting from the time the subject signs the informed consent form (ICF) until the end of treatment (EOT) visit, for 28 days after the last dose of CC-122 and for 90 days after the last dose of nivolumab, whichever occurs later. A thorough evaluation of medical conditions will be conducted during screening for eligibility. The safety variables for this study include AEs, safety clinical laboratory variables, 12-lead electrocardiograms (ECGs), left ventricular ejection fraction (LVEF) assessments, physical examinations, ophthalmologic exams, vital signs, ECOG PS, exposure to investigational product (IP), assessment of concomitant medications, and pregnancy testing for females of child bearing potential (FCBP).

Overview of Pharmacokinetic Assessments

Blood will be collected to estimate the PK of CC-122 when administered in combination with nivolumab and the PK of nivolumab when administered in combination with CC-122.

For CC-122, during the dose escalation part, intensive PK sampling will be performed in all subjects at multiple time points on Cycle 1 Day 15. For nivolumab, sparse PK (at predose and at the end of infusion) will be performed in all subjects on Cycle 1 Days 1 and 15. No PK will be collected during the dose expansion part.

[REDACTED]

Statistical Methods

Statistical analyses will be performed by study part, dose level/dosing regimen and/or HCC etiology as needed or applicable. All analyses will be descriptive in nature.

All summaries of safety data will be conducted using subjects receiving at least one dose of either IP (the Treated Population).

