	Screening Period	Treatment Period											Follow-up Period	Follow-up Period			
	Screening ^a	Cycle 1				Cycle 2				Subsequent Cycles		EOT	28 day follow-up	90 days follow-up	Disease Progression/ Survival/ Pregnancy		
Day ^b	-28 to -1	1 ^c	8	15	22	1	8	15	18	22	1	15					
Urinalysis	X (-14 to -1)					X					X						
Triplicate 12-lead electrocardiogram	X	X	X	X	X	X					X		X				
LVEF	X										X every 3 cycles		X				
Serum and/or urine β-hCG (in females of childbearing potential [FCBP] only)	X ^d (-14 to -1)	Prior to first dose of study drug and as PPRMP indicated.															
EFFICACY, PHARMACOKINETIC, AND PHARMACODYNAMIC ASSESSMENTS																	
		■		■													
	■	■	■	■	■	■		■	■		■						
	■																

Table 3: Table of Events (Continued)

	Screening Period	Treatment Period												Follow-up Period	Follow-up Period	
	Screening ^a	Cycle 1				Cycle 2					Subsequent Cycles		EOT			
Day ^b	-28 to -1	1 ^c	8	15	22	1	8	15	18	22	1	15		28 day follow-up	90 days follow-up	Disease Progression/Survival/Pregnancy
Fresh paired tumor biopsy	X ^f								D18 (+/- 7 days, preferably after 3 continuous days of CC-122 administration) ^g							
Tumor evaluation (CT or MRI)	X (-28 to -1)	RECIST 1.1 Every 8 weeks (±7 days) for the first 10 months, then every 12 weeks (±7 days), until death, lost to follow up, withdrawal of consent, progression or start of new anticancer therapy. See Section 6.5.1 irRECIST: At time of RECIST 1.1 progression if subject continues on treatment beyond progression. Additional evaluations should be performed at the time of rescan 4-6 weeks after RECIST 1.1 progression, and then again per standard of care. See Sections 6.5.2 and 6.5.4														
Alpha-fetoprotein	X	X				X					X		X			
INVESTIGATIONAL PRODUCT																
Administer CC-122		5/7 days continuously														
Administer nivolumab		Q2W														
CC-122 accountability		X	X	X	X	X	X	X		X	X	X	X			
Nivolumab accountability		Q2W												X ^h		X ^h
FOLLOW-UP																
Survival follow-up																Every 3 months (+/- 7 days)

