6.5. Efficacy Assessments

Tumor assessments will be performed at screening (up to 28 days before the start of study treatment), every 8 weeks (± 7 days) for the first 5 evaluations (through Month 10), thereafter every 12 weeks (± 7 days), regardless of treatment status. Tumor assessments should also be performed at any time, if clinically indicated. Tumor assessments should continue at the defined schedule until radiologic disease progression or the start of new anticancer therapy, beyond the end of treatment if necessary.

Response will be assessed using RECIST 1.1 (investigator assessment), and irRECIST as an exploratory assessment. An independent review of efficacy results may take place at any time at the discretion of the study Sponsor. Other exploratory efficacy variables, such as ECOG PS, AFP reduction, etc, will be summarized as well.

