6.5.4. Assessment of Response According to Immune-Related Response Criteria (irRECIST)

Evaluation of response will also be performed using irRECIST guidelines as an exploratory, but not treatment-determining, assessment. Evaluation via irRECIST will begin if treatment is continued beyond RECIST 1.1 documented progression. Additional details and definitions of irRECIST are found in Appendix C in Section 18.3.

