1. JUSTIFICATION FOR AMENDMENT

Significant changes included in this amendment are summarized below:

1. Per Food and Drug Administration (FDA) request on Investigator Brochure (IB) Edition 9, protocol was updated to include standard Cytochrome P450 (CYP) interaction language in alignment with all CC-122 studies.

Revised Sections: 8.2.

2. Updates to exclusion criteria.

Exclusion criteria #1 was updated to exclude all subjects who have had prior treatment with regorafenib. This change is based on the recent FDA approval of regorafenib for hepatocellular carcinoma (HCC) in the second line setting in order to maintain the homogeneity of the patient population.

Exclusion criteria #3 was updated to exclude any subjects with systemic therapy in the 4 weeks prior to starting investigational product in order to allow for an appropriate wash out period for any prior therapies.

Exclusion criteria #15h was changed from >100 pg/mL to >300 pg/mL to allow for inclusion of subjects with brain natriuretic peptide (BNP) between 100-300 pg/mL with cardiologist evaluation (specified under section 15.h.a). This change was made to allow subjects at low cardiac risk to be enrolled in the trial despite slightly elevated BNP. This language was updated in alignment with existing wording in other CC-122 protocols (eg, CC-122-ST-001).

Revised Sections: 4.3.

3. Due to the incidence of rash (and subsequent dose limiting toxicities) observed during the dose escalation portion of the study, language was added to the protocol to provide guidelines on the management of Grade 1 and Grade 2 rash. Rash is known to be a potential overlapping toxicity between CC-122 and nivolumab and these guidelines are being implemented to help mitigate the risk of these rashes reaching Grade 3 or higher.

Revised Sections: Table 6, Table 8, 7.10.4.8 (added).

4. Per Celgene protocol template and Informed Consent Form (ICF) template, updates to pregnancy language as defined by Drug Safety for teratogenic compounds (including CC-122).

Revised Sections: 10.4, 10.4.1, 10.4.2.

Minor changes included in this amendment are summarized below:

Minor editorial changes throughout.

Revised Sections: Global

Addition of Celgene Therapeutic Area Head name and Title.

Revised Section: Celgene Therapeutic Area Head Signature Page

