Protocol Summary was updated to include withdrawal of consent as a reason why subjects would not be followed for tumor evaluation until progression. This update was made for consistency with section 3.2.

Revised Section: Protocol Summary (Length of Study)

Clarification of language surrounding when archival tumor biopsies may be accepted in lieu of fresh tumor biopsies.

[REDACTED]

[REDACTED]

Revised Sections: 4.3.

Clarification of wording surrounding pregnancy testing requirements to include serum and/or urine testing according to the Pregnancy Prevention Risk Management Plan (PPRMP).

Revised Sections: Table 3, 6.1, 6.2, 6.3.

Clarification of wording surrounding the timing of Immune-related Response Evaluation Criteria in Solid Tumors (irRECIST).

Revised Sections: Table 3, 6.5.4.

Updated screening procedures to require hepatitis B virus (HBV) and hepatitis C virus (HCV) viral load at screening for all subjects to ensure consistency with table of events.

Revised Sections: 6.1.

Updated text of protocol for consistency with Protocol Summary to include that an independent review of efficacy results may take place at any time.

Revised Sections: 6.5.

Added text to clarify that CC-122 should not be taken at home on days when predose assessments are scheduled for consistency with Section 6.6.1 Pharmacokinetics of CC-122.

Revised Sections: 6.7, 6.8.3.

Updated text to reference the Summary of Product Characteristics (SmPC) for additional information regarding potential adverse events with nivolumab.

Revised Sections: 7.10.4.4.

Additional references were added with revisions and/or new information: Flockhart, Postow and Villadolid.

Revised Sections: 7.10.4.8, 8.2, 17

Changed text to clarify that a nivolumab overdose (on an infusion rate basis) is now defined as “any rate faster than the rate specified in the local label”. This was changed from “any rate faster than the protocol specified rate”.

Revised Sections: 7.11.

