Duration of SD must meet minimum duration for at least 6 weeks if the BOR is SD. If the minimum time for a best response of SD is not met, the subject's best response depends on the subsequent assessments.

For example:

- A subject who has SD at the first assessment, PD at the second but does not meet minimum duration for SD, will have a best response of PD. PD assessment does not

required to be confirmed. A subject who has SD at the first assessment and is then lost to follow-up would be considered not evaluable.

Confirmed BOR – RECIST 1.1

Confirmed BOR is derived using Table 5 to confirm the best response. Confirmation of response requires repeat assessment of response (CR or PR) at the next scheduled scan more than 4 weeks following the first assessment meeting response criteria. If best overall response is SD, it must meet the minimum duration of 6 weeks. If the minimum time for a best response of SD is not met, the subject's best response depends on the subsequent assessments.

irBOR – irRECIST

In irRECIST, the determination of the adaptation of the immune-related unconfirmed best overall response (irBOR) is the single best immune-related response of overall response across all time points (post-baseline) evaluated by investigator using irRECIST criteria defined in Table 4. The order in which responses are rated are irCR, irPR, irSD, irPD, irNE. For example if a subject has overall responses of irPR, irSD and irCR, the unconfirmed irBOR would be irCR. The same minimum duration of SD required in RECIST 1.1 must be met if the best overall response is irSD.

Objective Response Rate (ORR) and Disease Control Rate (DCR)

Unconfirmed ORR, confirmed ORR, DCR and sustained DCR will be derived separately for investigator RECIST 1.1 and irRECIST assessment [REDACTED]

Table 6: ORR and DCR Derivation rules

Endpoint	Confirmed	Criteria	Derivation
ORR	Yes	RECIST 1.1	Confirmed BOR of CR or PR
	No	RECIST 1.1	Unconfirmed BOR of CR or PR
	No	irRECIST	Unconfirmed irBOR of CR or PR
DCR	No	RECIST 1.1	Unconfirmed BOR of CR, PR or SD
	No	irRECIST	Unconfirmed irBOR of CR, PR or SD
Sustained DCR	No	RECIST 1.1	Unconfirmed BOR of CR, PR or SD (duration of SD \geq 16 weeks)
	No	irRECIST	Unconfirmed irBOR of CR, PR or SD (duration of SD \geq 16 weeks)

Abbreviations: BOR = best overall response; CR = complete response, SD = stable disease, PR = partial response, ir = immune related

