Urinalysis	X (-14 to -1)					X					X						
Triplicate 12-lead electrocardiogram	X	X	X	X	X	X					X		X				
LVEF	X										X every 3 cycles		X				
Serum β-hCG (in FCBP)	X (-14 to -1)	As PPRMP indicated – to be updated according to PPRMP															
Urine β-hCG (females of childbearing potential [FCBP] only)	X ^d (-14 to -1)	As PPRMP indicated – to be updated according to PPRMP															
EFFICACY ASSESSMENTS																	
PK samples (Intensive or sparse, multiple time points)		X		X													
	■	■	■	■	■	■		■	■		■						
	■																

	Screening Period	Treatment Period											Follow-up Period	Follow-up Period			
	Screening ^a	Cycle 1				Cycle 2					Subsequent Cycles			EOT	28 day follow-up	90 days follow-up	Disease Progression/Survival/Pregnancy
Day ^b	-28 to -1	1 ^c	8	15	22	1	8	15	18	22	1	15					
Fresh paired tumor biopsy	X ^f								D18 (+/- 7 days, preferably after 3 continuous days of CC-122 administration) ^g								
Tumor evaluation (CT or MRI)	X (-28 to -1)	RECIST 1.1 and irRECIST algorithm: Every 8 weeks (±7 days) for the first 10 months, then every 12 weeks (±7 days), until death, lost to follow up, progression or start of new anticancer therapy. See Sections 6.5.1 and 6.5.2 in the protocol															
Alpha-fetoprotein	X	X				X					X		X				
INVESTIGATIONAL PRODUCT																	
Administer CC-122		5/7 days continuously															
Administer Nivolumab		Q2W															
CC-122 accountability		X	X	X	X	X	X	X		X	X	X	X				
Nivolumab accountability		Q2W											X ^h			X ^h	
FOLLOW-UP																	
Survival follow-up																	Every 3 months (+/- 7 days)

Abbreviations: β-hCG = beta human chorionic gonadotropin; BNP = brain natriuretic peptide; CBC = complete blood count; CK = creatine kinase; CT = computed tomography; ECOG PS = Eastern Cooperative Oncology Group Performance Status; EOT = End of Treatment; FCBP = females of child bearing potential; FFPE = formalin-fixed, paraffin embedded; fT4 = free T4; HBV = hepatitis B virus; HBsAg = hepatitis B surface antigen; HBeAg = hepatitis B e antigen; HBsAb= hepatitis B surface antibody; HBeAb = hepatitis B e antibody; HBcAb = hepatitis B core antibody; HCVAb = HCV antibody; HCV = hepatitis C virus; IG = immunoglobulin; INR = international normalized ratio;

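### If sites follow the protocol's start rule for irRECIST, the SAP's irORR and irDCR can fall below unconfirmed ORR and DCR as a collection artefact; the number affected and the net direction are unknown

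*SAP*

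**What the plan says.** **When irRECIST is assessed, protocol.** Section 6.5.4: "Evaluation via irRECIST will begin if treatment is continued beyond RECIST 1.1 documented progression". Table 3 agrees: "irRECIST: At time of RECIST 1.1 progression if subject continues on treatment beyond progression", with further evaluation at a rescan 4 to 6 weeks later and then per standard of care. Two other places name irRECIST without a start rule: the Protocol Summary ("Tumor response will also be determined by the Investigator based on irRECIST") and section 6.5 ("Response will be assessed using RECIST 1.1 (investigator assessment), and irRECIST as an exploratory assessment").

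**When irRECIST is assessed, SAP.** Section 10.1 has investigators apply both criteria to treated subjects, with no limit on timing. The tumor evaluation row of Table 14 reads "RECIST 1.1 and irRECIST algorithm: Every 8 weeks (±7 days) for the first 10 months". That row stops at progression, among other endings, and cites protocol 6.5.1 and 6.5.2 but not 6.5.4.

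**How the results are derived.** SAP 10.2 defines irBOR as the single best "response across all time points (post-baseline) evaluated by investigator using irRECIST criteria", ranked from irCR down to irNE. In SAP Table 6, irORR is an unconfirmed irBOR of CR or PR, and irDCR adds SD. Both are reported with exact 95% confidence intervals on the Safety and EE Populations. No visible SAP text carries a RECIST 1.1 response into irBOR or limits the denominator to subjects with an irRECIST call.

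**Whether they will be run.** SAP section 15 item 2 cancels the expansion phase and drops exploratory efficacy analyses limited by the data, without naming them. SAP section 10 still specifies the irRECIST outputs in full.

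**The concern.** The protocol's collection rule and the SAP's derivation do not fit together. The protocol ties irRECIST to treatment beyond progression; the SAP treats it as a parallel reading available for every subject. Followed literally, the two count a durable RECIST responder as an irRECIST non-responder.

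The missing calls would not be a random subset, because subjects who never progress are among those without one. A reader who saw irORR below unconfirmed ORR might take it as a finding about immune-related response, when it could reflect only who had an irRECIST form. Efficacy is tabulated by dose cohort, so one subject can move a cohort's figure a long way.

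**Working it through.** The documents state no irORR, irDCR or share treated beyond progression, so there is no planned figure to reproduce.

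**Step 1. Who has an irRECIST call if sites follow protocol 6.5.4 and Table 3?**

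| Course under RECIST 1.1 | irRECIST calls | Effect under SAP 10.2 |
|---|---|---|
| CR, PR or SD, never progresses | None | In denominator, cannot enter numerator |
| CR, PR or SD, then PD, stops treatment | None | Same |
| CR, PR or SD, then PD, continues | From PD onward only | Counted only if still rated irCR or irPR (or irSD, for irDCR) from then on |
| PD, continues, later responds by irRECIST | From PD onward | Adds to numerator |

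The irNE category can hold the first two types but does not restore their response.

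**Step 2. What would complete collection give?** Under SAP Table 4 a new lesion is RECIST PD. Before RECIST PD there is therefore no new lesion, and the total measured tumor burden equals the target-lesion sum. A RECIST CR or PR then also meets irCR or irPR, so complete data give irORR no lower than unconfirmed ORR. RECIST CR also requires tumor marker normalisation; this can shift the irCR/irPR split but not irORR.

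**Step 3. Loss per affected subject = 100/N.**
- N=20 (Phase 1 size in protocol 4.1 and 9.3): 100/20 = 5.0 points. Protocol 7.2.1 says 20 to 30; at N=30, 100/30 = 3.3.
- Cohort of 6: 100/6 = 16.7 points. Cohort of 3: 100/3 = 33.3.

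**Step 4. Illustration, assumed inputs.** Let R be the unconfirmed RECIST responders, f the share of them who progress and continue treatment, k the share of those still rated irCR or irPR from then on, and m the subjects who respond by irRECIST only after RECIST PD.

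irORR collected under the protocol rule = (R × f × k + m)/N. With complete collection it is (R + m)/N.

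Take N=20 and R=4, so unconfirmed ORR is 4/20 = 20.0% (Clopper-Pearson 95% CI 5.7–43.7):

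| Assumption | m=0 | m=2 |
|---|---|---|
| f=0 | 0/20 = 0.0% (0–16.8) | 2/20 = 10.0% (1.2–31.7) |
| f=0.5, k=0.5 | 1/20 = 5.0% (0.1–24.9) | 3/20 = 15.0% (3.2–37.9) |
| f=1, k=0.5 | 2/20 = 10.0% (1.2–31.7) | 4/20 = 20.0% (5.7–43.7) |
| f=1, k=1 | 4/20 = 20.0% (5.7–43.7) | 6/20 = 30.0% (11.9–54.3) |
| Complete collection | 4/20 = 20.0% | 6/20 = 30.0% |

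The shortfall against complete collection is R(1 − f × k)/N, which is never negative. Against unconfirmed ORR the result can be lower, equal or higher, depending on m.

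DCR works the same way. With an assumed 12/20 = 60.0% (36.1–80.9) controlled and 4 of them without a call, those subjects contribute at most (12 − 4)/20 = 40.0% (19.1–63.9).

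**Step 5. irPFS and irTTP.** SAP 10.5.1 and 10.5.2 use the first date of PD as irRECIST defines it, which is not worded as an investigator call. On a plain reading, a scanned subject without progression is censored at the last adequate tumor assessment. For a subject who stops at RECIST PD with no irRECIST evaluation, target growth of at least 20% and 5 mm from nadir meets the SAP Table 4 irPD criteria from recorded diameters. The unclear case is mainly progression by new lesions: a new measurable lesion is RECIST PD but not necessarily irPD.

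**The case against.** **The calls may exist.** SAP 10.1, SAP Table 14, the Protocol Summary and protocol 6.5 can all be read as irRECIST for every subject. SAP section 10 lists tumor burden at each visit, and SAP 10.2 plots it for all subjects with non-missing values. Protocol Appendix C, to which 6.5.4 refers for details, is not in the text reviewed. This stands: what sites recorded is not shown. It does not remove the need for a rule, since 6.5.4 and Table 3 are explicit and the SAP has no fallback.

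**The endpoints are low-stakes.** irRECIST is exploratory, the analyses are descriptive, and section 15 item 2 may already have dropped these tables. This stands and limits the weight of the point.

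**Stronger readings that a reader might infer, and that the documents do not support:**
- *That Table 14 causes the shortfall.* If Table 14 were followed, calls would exist at every scheduled scan up to progression. The artefact comes from protocol 6.5.4 and Table 3 combined with SAP 10.2. Aligning Table 14 alone changes no result.
- *That irORR and irDCR are biased downward.* This holds only if sites followed the protocol rule, and responses after RECIST PD add to irORR.
- *That Amendment 2 changed collection, so earlier subjects have fuller data.* Some subjects were treated before it ("Due to the incidence of rash (and subsequent dose limiting toxicities) observed during the dose escalation portion of the study"), but its log calls the irRECIST item a minor change: "Clarification of wording surrounding the timing of Immune-related Response Evaluation Criteria in Solid Tumors (irRECIST". The log does not say that collection changed. That Table 14 predates the amendment is at most an inference.
- *That a subject who stops at RECIST PD has no irPD date.* Recorded lesion data may supply one, as Step 5 shows.

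**Conclusion.** The point holds conditionally. If sites collected irRECIST as protocol 6.5.4 and Table 3 direct, SAP 10.2 as written can put irORR and irDCR below unconfirmed ORR and DCR purely because calls are missing. The firm size is 100/N points per affected subject; the responder counts and shares in Step 4 are assumptions. The number affected and the net direction cannot be determined from the documents.

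The mismatch between Table 14, which ends irRECIST at progression, and the protocol, which starts it there, is a separate inconsistency in current text. The primary RECIST 1.1 ORR is untouched. This is worth correcting before the irRECIST tables are produced, but it does not threaten the trial's main result.

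**What to change.** 1. In SAP 10.2, derive irBOR for all treated subjects, time point by time point. Use the investigator irRECIST call where one is recorded; otherwise use the RECIST 1.1 response at scans before RECIST PD. From RECIST PD onward, use the irRECIST evaluations.
2. For RECIST PD with no irRECIST evaluation, apply the SAP Table 4 irPD criteria to recorded lesion data for irPFS and irTTP. Where that is not possible, mainly progression by new lesions, use one pre-specified convention and report how many subjects it affects. Do not equate RECIST PD with irPD automatically.
3. Reconcile SAP Table 14 with protocol Table 3 and 6.5.4, including where the irRECIST schedule starts and ends.
4. If the irRECIST analyses are dropped under SAP section 15 item 2, name them there.

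The cost is SAP wording, one derivation rule and a little programming. No new scans are needed, and recorded irRECIST evaluations are kept. The limit is that the documents do not show whether new-lesion diameters were recorded for subjects who stopped at RECIST PD, so classification there may be incomplete.
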